**Psychophysiological and Cognitive Biomarkers of Ketamine's Antidepressant Effects
(Protocol 2015P002397)**

NCT02669043

Version Date: 12/13/2016

Detailed Protocol:

I. Background and Significance

Establishing remission of major depressive disorder (MDD) often takes weeks to months to achieve on traditional monoamine-based antidepressants. Only about one-third of individuals with MDD remit on an initial course of treatment, with even lower rates of remission among individuals with certain depressive subtypes, such as anxious depression. There is a compelling and widely acknowledged need for antidepressants that work more rapidly, that recruit novel, non-monoamine mechanisms, and that target subtypes of depression that respond poorly to current antidepressants. Towards this end, single subanesthetic infusions of ketamine (an ant glutamatergic medication) have been shown to improve the symptoms of depression in a rapid (within hours), robust (across many symptoms), and relatively sustained manner in patients with treatment-resistant depression (TRD).(1) Ketamine may have greater efficacy for forms of depression not well treated by current agents—especially *anxious depression*.(2) Low dose parenteral ketamine has now been studied for difficult to treat depressive disorders by numerous research groups and off label administration of ketamine is increasingly available in some clinical settings.

[figure not shown]
There is a widely recognized need for developing biomarkers that may predict response to rapidly acting antidepressant agents such as ketamine. The identification of biomarkers of treatment response to rapidly-acting therapeutics for depression is likely to advance targeted drug development and the goal of personalizing depression treatment. The current protocol is aimed at further delineating potential biomarkers of ketamine's effects among individuals with treatment-resistant anxious depression, as well as using putative biomarkers to diagnose depression subtypes (i.e., anxious depression).

Background and Preliminary

Results: Ketamine and Anxious Depression.

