As described earlier, dysfunction in reward processing may be critical in the pathophysiology of anxious depression (7,8). In order to examine the spectrum of reward dysfunction in depressed patients, as well as to test the extent to which cognitive deficits in reward processing predict ketamine's antidepressant effects, we will conduct a pre-treatment probabilistic reward task, an objective measurement of participants' ability to modulate behavior as a function of rewards. Clinically, depressed patients have a deficit in reward learning (a construct of the so-called RDoC [Research Domain Criteria] positive valence domain), as they have difficulty modifying their behavior despite positive reinforcement.(8) In one previous probabilistic reward task study, pre-treatment inability to modify reward learning in depressed patients predicted continued depressive symptoms at 8-weeks after treatment was initiated.(23) In view of ketamine's effect on the NMDA receptor and its relationship to reward processing, we hypothesize that greater reward dysfunction will predict response to ketamine.

In summary, we found that subjectively-diagnosed anxious depression predicts a greater antidepressant response to ketamine compared to nonanxious depression. Aberrant brain circuitry between the bed nucleus of the stria terminalis and the reward circuitry may contribute to the psychopathology observed in the anxious-depression phenotype, and might be the targets that account for ketamine's superior antidepressant efficacy among individuals with this depressive subtype. Therefore, higher pre-treatment psychophysiological (i.e., anxiety-potentiated startle magnitude) and cognitive (i.e., reward dysfunction) measures of anxiety in depressed patients may serve as biomarkers that can clinically predict better treatment response to ketamine and that reflect the activity of specific circuits that could be targeted for future drug development.

II. Specific Aims

The overall aims of this protocol are to study biomarkers for diagnosis and treatment response in mood disorders. Specifically:

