Specific Aim #1: Determine the extent to which objective measures of anxiety are related to subjective measures of anxiety in patients with mood dysregulation. Our *working hypothesis* is that patients with clinically-diagnosed anxious depression will have higher objective measures of anxiety (anxiety-potentiated startle responses and lower reward responsiveness) compared to those with nonanxious depression.

Specific Aim #2: Determine the extent to which these biomarkers predict response to ketamine. Our *working hypothesis*, based on pilot data and previous work, is that higher pre-treatment psychophysiological measures of anxiety-potentiated startle and lower reward responsiveness on cognitive measures will correlate with a better antidepressant response to ketamine.

Specific Aim #3: Determine the effect of ketamine on the biomarkers. Our *working hypothesis* is that greater reductions in anxiety-potentiated startle magnitude, and greater improvements in measures of reward responsiveness, will be found among ketamine responders compared to nonresponders.

III. Participant Selection

Inclusion Criteria: Patients

Patients will:

- 1) be 18-64 years old,
- 2) read, understand, and provide written informed consent in English,
- 3) meet criteria for a primary psychiatric diagnosis of Major Depressive Disorder (MDD) for ≥ 4 weeks, according to the Mini International Neuropsychiatric Interview (M.I.N.I.) and have a Hamilton Depression Rating Scale (HDRS-28) total score ≥ 20 ; depression may have started at any time point in their life, and certain co-morbid diagnoses (e.g., anxiety disorders) will be allowed,
- 4) have a history ≥ 1 failed medication trial during the current depressive episode (per the MGH Antidepressant Treatment History Questionnaire),
- 5) be on a stable adequate dose of an FDA-approved antidepressant medication for ≥ 28 days prior to Study Phase II (see medication inclusion/exclusion list),
- 6) maintain a treating doctor who is in agreement with study participation,
- 7) have a reliable chaperone to accompany them home following the completion of Visit 3 (the ketamine infusion day),
- 8) be generally healthy, as assessed by medical history, physical examination (including vital signs), clinical laboratory evaluations, and electrocardiogram (EKG),
- 9) be of non-childbearing potential or use of an acceptable form of birth control (females only).

Exclusion Criteria: Patients

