Testing of Hypotheses: Statistics and Data Analysis

Specific Aim #1: Objective and subjective measures of anxiety will be positively correlated with each other. A primary analysis will examine Pearson correlations between subjective measures of anxiety (i.e., the HDRS Anxiety-Somatization Factor Scale, HAM-A, and CUDOS-A) and eye-blink startle response. Similarly, we will examine correlations between subjective anxiety and reward responsiveness. We will analyze the data to ensure that linearity exists. If linearity does not exist, we will conduct comprehensive sub-analyses to find the best way to characterize the relationship of all data. For example, we will use covariates (e.g., clinical descriptors such as treatment failures) to determine their role in creating non-linearity.

Specific Aim #2: Greater psychophysiological and cognitive objective measures of anxiety will predict better antidepressant response to ketamine, regardless of subjective depression symptoms. We will use a nonlongitudinal linear regression model to assess the extent to which the combination of pre-treatment psychophysiological (e.g., anxiety-potentiated eye-blink startle) and cognitive reward processing (high versus low reward responsiveness) predict the antidepressant treatment response to ketamine (Visits 3 and 4). Antidepressant response to ketamine will be defined as a $\geq 50\%$ improvement in HDRS scores (primary dependent outcome measure).

Specific Aim #3: In ketamine responders, psychophysiological measurements will show a significantly larger decreases in magnitude compared to ketamine nonresponders; greater improvements will be seen in cognitive reward processing measures in ketamine responders. We will use longitudinal analyses (linear mixed effects random regression models) to analyze the effect of ketamine on

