the biomarkers. These models account for the correlation of observations from the same individual. For the change in startle magnitude post-ketamine, the model will include the change in startle magnitude as the outcome, and time (Visit 2 and 4) as the predictor. For the change in reward processing post-ketamine, the model will include the change in reward processing as the outcome, and time (Visit 2 and 4) as the predictor. The coefficient for the correlations in this model quantifies the rate of change in the psychophysiological and cognitive measures associated with a change in depressive symptoms. A coefficient significantly different from zero indicates that changes in the clinical measures of depression are associated with changes in psychophysiological and/or cognitive measures. We will also perform between-group comparisons of measurements for responders vs. nonresponders. All models will be fit using SAS software, $\alpha=0.05$, two-tailed.

Sample Size Determination:

The sample size for Aims #1 and #2 was calculated using the G*Power Sample Size calculator (Version 3.9.1.2; downloaded from <http://www.gpower.hhu.de>) and was based on findings from a *post-hoc* analysis of the antidepressant treatment response to ketamine in anxious versus nonanxious depressed patients, where anxious depression predicted a better response to open-labeled ketamine.(6) The anxious depression effect size (Cohen's *d*) reached its maximum of $d=0.76$ on Day 2 post-infusion. With this, for Aims #1 and #2, we estimate requiring 58 patients with power >0.8 , $r=0.35$ and an $\alpha=0.05$, two-tailed, in order to reject the null hypothesis that there will be no correlations with baseline psychophysiological and cognitive measures between ketamine responders and nonresponders. For Aim #3, a sample size of 58 would allow us to detect a moderately-large effect size (Cohen's $d\geq 0.75$) for between-group comparisons. In order to account for potential drop-outs, we will recruit 70.

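### Aim #1's anxious versus nonanxious hypothesis has no matching analysis or group definition, and the sample-size null given for Aim #1 is about ketamine responders

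*Combined protocol and SAP*

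**What the plan says.** The Aim #1 objective in II. Specific Aims is dimensional: "Determine the extent to which objective measures of anxiety are related to subjective measures of anxiety in patients with mood dysregulation". The working hypothesis directly after it is categorical: "patients with clinically-diagnosed anxious depression will have higher objective measures of anxiety", namely startle and reward responsiveness, "compared to those with nonanxious depression".

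Section VI (Specific Statistical Methods, Specific Aim #1) restates the hypothesis without groups: "Objective and subjective measures of anxiety will be positively correlated with each other". The analysis follows that version: "A primary analysis will examine Pearson correlations between subjective measures of anxiety" (the HDRS Anxiety-Somatization factor, HAM-A and CUDOS-A) and eye-blink startle, with parallel correlations for reward responsiveness. The only between-group comparison in the section is responders versus nonresponders, under Aim #3.

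Sample Size Determination gives one calculation for Aims #1 and #2: 58 patients, power above 0.8, r=0.35, two-tailed alpha 0.05. The null to be rejected is "no correlations with baseline psychophysiological and cognitive measures between ketamine responders and nonresponders".

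On purpose, section II opens with "The overall aims of this protocol are to study biomarkers for diagnosis and treatment response in mood disorders". Section I likewise names diagnosis of depression subtypes, specifically anxious depression, as a use of the biomarkers.

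**The concern.** The plan gives Aim #1 an objective that its analysis can answer, a working hypothesis that its analysis does not test, and a sample-size null that belongs to a different question. Responder status is known only after ketamine, whereas Aim #1 relates anxiety scores to objective measures and does not involve treatment response.

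The group hypothesis also cannot be tested as written, because the documents do not say what makes a patient clinically anxious or nonanxious. With three anxiety scales collected and no cut-off named, a rule could be chosen after the data are seen.

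At stake is interpretation. A significant correlation would leave the stated group difference unestimated. If it were then read as evidence that the biomarkers can diagnose the anxious subtype, no measure of separation between the groups would support that reading.

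**Working it through.** **Inputs.** From Sample Size Determination: N=58, r=0.35, two-sided alpha 0.05, power above 0.8; source effect d=0.76; detectable d of 0.75 for between-group comparisons (stated for Aim #3). From section I: the earlier sample had 15 anxious and 11 nonanxious patients. The split in this study is not stated, so 29:29 to 46:12 is assumed as a range; the earlier ratio scales to 33:25.

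**1. The plan's own figure.** N=58 reproduces as a two-group calculation.
- Conversion at equal groups: r = d/√(d²+4) = 0.76/√(0.5776+4) = 0.355, close to the stated 0.35.
- Two-sample t-test, 29 per group, d=0.75: noncentrality = 0.75 × √(29×29/58) = 2.856 on 56 df, power 0.801. At d=0.76 the power is 0.812.
- Point-biserial r=0.35: power 0.799 at N=58.

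The d=0.76 is a difference in antidepressant response between anxious and nonanxious patients, not a difference in startle or reward.

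**2. The planned Pearson correlation.** Fisher z: atanh(0.35) = 0.3654.
- Power at 58 = Φ(0.3654 × √55 − 1.960) = Φ(0.750) = 0.773.
- N for 80% power = ((1.960 + 0.842)/0.3654)² + 3 = 61.8, so 62.
- Simulation under bivariate normality gives power 0.781 at 58, and about 61 patients for 80%.

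**3. What a significant correlation implies for group separation.** The critical t on 56 df is 2.003, so the smallest significant |r| = 2.003/√(56 + 2.003²) = 0.259. Suppose the anxiety score and the biomarker are bivariate normal and the score is split at its median. The correlation with the group label is then a = r × √(2/π) = 0.798r, with d = 2a/√(1−a²) and AUC ≈ Φ(d/√2). Simulation agrees with these AUCs to two decimals.

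| r | a | d | AUC |
|---|---|---|---|
| 0.259 | 0.206 | 0.42 | 0.62 |
| 0.35 | 0.279 | 0.58 | 0.66 |

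**4. What an added group comparison could show.** Two-sample t-test, N=58, d=0.75:

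| Assumed split | Power, alpha 0.05 | d detectable at 80% power |
|---|---|---|
| 29:29 | 0.80 | 0.75 |
| 33:25 | 0.79 | 0.76 |
| 38:20 | 0.76 | 0.79 |
| 43:15 | 0.69 | 0.86 |
| 46:12 | 0.62 | 0.92 |

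With alpha 0.025 for each of startle and reward, power is 0.71 at 29:29 and 0.51 at 46:12. If the true effect is the d=0.58 implied by r=0.35 under the median split, power at 29:29 and alpha 0.05 is 0.59.

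**5. Precision of the AUC.** Hanley-McNeil at AUC 0.66 with 29:29: Q1 = 0.66/1.34 = 0.4925 and Q2 = 2×0.4356/1.66 = 0.5248. SE = √[(0.2244 + 28×0.0569 + 28×0.0892)/841] = 0.072, giving a 95% CI of about 0.52 to 0.80.

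**The case against.** The strongest defence is that the aim sentence asks how far objective and subjective measures are related, and a correlation answers exactly that. The analysis section restates the hypothesis in those terms, and Expected Outcomes/Results anticipates a moderate correlation. On this view one working-hypothesis sentence is a categorical paraphrase of a dimensional question, and the correlation is a close analogue that avoids the information lost by splitting a score. This stands, and it limits the point: a reader might infer that Aim #1 goes untested, but the documents do not support that.

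A reader might also infer that the sponsor will present a significant correlation as a diagnostic biomarker. No section says so. Diagnosis is a goal of the protocol as a whole and is not mentioned in the Aim #1 text. Expected Outcomes/Results speaks of adding to scarce information, and section VIII of groundwork for future studies. The supported statement is narrower: no planned analysis would bear out a diagnostic claim if one were made.

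Section IX describes the work as a physiological biomarker study rather than a clinical trial, and the primary clinical endpoint, HDRS-28 change, is untouched. That argues for a modest repair. It does not remove the gap: no section supplies the group comparison, the classification rule or an Aim #1 null.

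**Conclusion.** The point holds in a limited form. The Aim #1 group contrast has no analysis and no group definition, and the null stated for Aims #1 and #2 does not fit Aim #1. The correlational objective is addressed.

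Under bivariate normality and a median split, a just-significant correlation corresponds to d of about 0.42 and AUC 0.62, and the planned r=0.35 to d of about 0.58 and AUC 0.66. Significance is therefore compatible with weak separation. Converting these correlations directly with d = 2r/√(1−r²) would give larger values, but that formula is for a variable that is already a two-group label, and the planned scales are scores.

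A reader might infer that 58 is simply too few for the group contrast. That does not follow: power is 0.80 at d=0.75 with 29:29, falling to 0.62 at 46:12. The split is an assumption, however, and no startle or reward effect size in the documents supports d=0.75. For the Pearson test actually planned, 58 gives about 0.77 rather than above 0.8, a small shortfall. This should be corrected, but it does not threaten the study.

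**What to change.** 1. Keep the correlation as the primary Aim #1 analysis. In Sample Size Determination, separate Aim #1 from Aim #2 and state the Aim #1 null as no correlation between the subjective anxiety score and the biomarker. Note that for Pearson r=0.35 and two-sided alpha 0.05, 58 patients give power of about 0.77 by Fisher z, with 62 needed for 0.80.
2. Before analysis, write in one definition of anxious depression based on a scale already collected. The documents give no cut-off, so the sponsor must supply it. Add one comparison of anxious and nonanxious patients on startle and reward responsiveness, labelled secondary, reporting the mean difference and the AUC, each with a 95% CI.
3. Rest any statement about diagnosing the anxious subtype on that estimate and its interval, not on a significant correlation.

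The cost is wording plus one secondary analysis, with no new patients, visits or measurements. The downside is one more reported comparison of limited precision, with power depending on a split that is not yet known. The wide AUC interval is a reason to report it, since it shows how little can be said about diagnosis at this sample size.

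### Aim #2 asks how far the combined biomarkers predict response, but the plan has no optimism correction and no measure of discrimination, so any predictive strength read from the fit is biased upward

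*Combined protocol and SAP*

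**What the plan says.** The aim (Section II, Specific Aim #2) is quantitative: "Determine the extent to which these biomarkers predict response to ketamine". The analysis text for the same aim in Section VI repeats this: "We will use a nonlongitudinal linear regression model to assess the extent to which the combination" of pre-treatment startle and reward measures predicts response, where response is an HDRS improvement of at least 50%. All models are tested at alpha 0.05, two-tailed.

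The closing summary of Section I gives the hoped-for use: higher pre-treatment measures "may serve as biomarkers that can clinically predict better treatment response to ketamine".

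The sample size (Section VI, Sample Size Determination) is set for a test of association. It says "we estimate requiring 58 patients with power >0.8" at r = 0.35, "in order to reject the null hypothesis that there will be no correlations with baseline psychophysiological and cognitive measures". The effect comes from a post-hoc comparison of anxious and nonanxious depression, whose Cohen's d "reached its maximum of $d=0.76$ on Day 2 post-infusion".

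Section V describes a single open-label group. Section VI mentions no hold-out sample, cross-validation, bootstrap, shrinkage or adjusted R², and names no R², AUC, sensitivity or specificity. The predictors are not fixed: startle is given only as an example, and reward responsiveness is to be split into high and low without a stated cut.

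**The concern.** Least squares chooses the coefficients that fit the observed patients best. The strength of prediction read from those patients is therefore higher, on average, than the same equation would achieve in others. In a sample of 58 with modest true associations, the difference is not negligible.

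A p-value does not fill the gap. A coefficient can differ from zero while the model separates responders from nonresponders poorly. The aim asks for the extent of prediction, and Section I looks ahead to clinical use. The plan as written offers either an unvalidated fit or a significance test as the answer, and neither tells a reader how well the markers would work in the next patient.

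**Working it through.** **Inputs.** n = 58, r = 0.35, alpha 0.05 two-tailed and d = 0.76 are from Section VI. The number of predictors p is not stated. I take p = 2 (one startle and one reward measure) as the base case and vary it. The response rate is not stated either, so I use 30%, 50% and 70%.

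**The plan's own figure.** r = d/√(d² + 4) = 0.76/√4.5776 = 0.355, which agrees with the stated 0.35. A two-sample t-test with d = 0.76 needs 29 per group, or 58. A point-biserial correlation test at r = 0.35 needs 59 (power 0.799 at 58), and at 0.355 it needs 57. The stated 58 is reproduced to within rounding of r, as the size for a test of association.

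**Optimism in R².** The expected R² of the fitted equation in new patients is approximately

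1 − (1 − R²)(1 + 1/n)(n − 2)/(n − p − 2).

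With R² = 0.35² = 0.1225 and n = 58:

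- p = 1: 1 − 0.8775 × (59/58) × (56/55) = 0.091
- p = 2: 1 − 0.8775 × (59/58) × (56/54) = 0.074
- p = 3: 1 − 0.8775 × (59/58) × (56/53) = 0.057

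If each of two independent markers has r = 0.35, then R² = 2 × 0.1225 = 0.245, and the result is 1 − 0.755 × (59/58) × (56/54) = 0.204.

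Simulation of 4,000 trials per setting (normal predictors, continuous outcome) gives:

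| Setting | Apparent R² | New-patient R² | Ratio | Apparent vs new-patient correlation |
|---|---|---|---|---|
| 1 predictor, R² = 0.1225 | 0.136 | 0.091 | 1.5 | 0.35 vs 0.35 |
| 2 predictors, R² = 0.1225 | 0.151 | 0.075 | 2.0 | 0.373 vs 0.324 |
| 3 predictors, R² = 0.1225 | 0.165 | 0.056 | 3.0 | 0.392 vs 0.301 |
| 2 predictors, R² = 0.245 | 0.263 | 0.204 | 1.3 | 0.504 vs 0.480 |

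In the two-predictor base case the inflation on the correlation scale is 0.373/0.324 = 1.15, or about 15%.

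**Binary outcome, as Section VI defines response.** With two predictors and R = 0.35, the R² ratio is 1.92 to 1.99 across the three response rates. Apparent AUC is 0.714 to 0.735 and new-patient AUC 0.684 to 0.703, a loss of about 0.03. With three predictors the loss is about 0.05 to 0.06 (for example 0.727 vs 0.674 at a 50% response rate).

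**Selection.** The protocol also records heart rate and skin conductance, and names two main variables for the reward task, so more than two candidates exist. If the best two of four are kept at R² = 0.1225, apparent R² is about 0.16 and new-patient R² about 0.04, a ratio of about 3.6 or more. With eight candidates, new-patient R² is close to zero.

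**What a just-significant result means.** The critical r at n = 58 is 2.003/√(2.003² + 56) = 0.259. Treated as a point-biserial correlation with equal groups, d = 2r/√(1 − r²) = 0.54, AUC = Φ(d/√2) = 0.65, and correct classification is Φ(d/2) = 61%. The same formulas at r = 0.35 give d = 0.75 and AUC 0.70. If instead 0.35 is the correlation with a continuous outcome that is then split at its mean, the AUC is about 0.66.

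**The case against.** The working hypothesis of Aim #2 is that the markers will correlate with response, and the sample-size null is no correlation. Testing that needs no out-of-sample validation. The Section I sentence on clinical prediction is background and hedged, and Section IX describes a physiological study of biomarkers, not a clinical trial. All of this stands. The coefficient tests are sound as tests of association, and nothing here changes n.

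A reader might infer that the trial will report a predictive strength about twice the true one. The documents do not support this as a general statement. The plan names no strength measure, so there is no defined figure to halve. The factor of two holds for R², with two fixed predictors and a combined R of 0.35. On the correlation scale the inflation there is about 15%, and with a single predictor it disappears. Measured against the population R² of 0.1225, the fitted 0.151 is too high by only about 0.03; the rest of the gap is the cost of estimating the coefficients in 58 patients.

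A reader might also infer that the plan intends to declare a clinical predictor on p < 0.05. No section says so.

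The objection does not remove the mismatch. Both the aim and its analysis sentence ask for the extent of prediction by a combination of markers, which a test of zero association does not measure. The uncertainty also runs in both directions: the planning effect was the largest over the follow-up times, so a smaller true effect, and with it a larger R² ratio, is plausible.

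**Conclusion.** The point holds in a conditional form. Aim #2 asks for predictive strength, and the plan provides only a model fitted and evaluated in the same 58 patients, with no optimism correction and no measure of discrimination. The upward direction of the bias in apparent R² is certain.

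Its size rests on assumptions the documents do not settle. For two pre-specified predictors and a combined R of 0.35, it is about 0.15 against 0.075 in R², 0.37 against 0.32 in multiple R, and about 0.03 in AUC. The R² ratio is about 1.3 with stronger markers, 1.5 with one predictor, about 3 with three, and more with selection. Separately, a result that only just reaches significance corresponds to an AUC of about 0.65 with equal groups, which is weak support for clinical prediction.

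This limits what can be concluded from Aim #2. It does not invalidate the planned test or the sample size.

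**What to change.** In the Specific Aim #2 text of Section VI:

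1. Keep the regression coefficients and their tests, labelled as tests of association.
2. Fix in advance which startle and reward variables enter the model, including any cut for high and low reward responsiveness. The correction below cannot be carried out properly until this is done.
3. For the stated response of at least 50% HDRS improvement, report the bootstrap optimism-corrected AUC with a 95% confidence interval, repeating every model-building step in each resample. If HDRS-28 change is also modelled, report the optimism-corrected R² for it.
4. Base any statement that the biomarkers predict response clinically on the corrected values. Otherwise, word the Aim #2 conclusion as association.

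The cost is a few sentences in the plan and a little more analysis code, with no new data and no change to n. The reported strength will look less favourable.
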